Study Design Overview: We propose to study the separate and combined effects of the FDA-approved cannabinoid dronabinol (Marinol) and the prototypical opioid hydromorphone (Dilaudid). Following telephone and screening to establish study eligibility, a cohort of **n=100** adults with knee osteoarthritis (KOA) will complete four different within-subject experimental sessions. Participants will complete one of two Phases, receiving either a 4mg or 2mg dose of hydromorphone. Randomization will be split equally across the two Phases. During each session, participants will complete baseline QST, questionnaires, and a neurocognitive battery. Oral hydromorphone will be administered in the first session. Subsequent sessions will consist of 1 of 3 conditions, and session order will be randomized and counter-balanced. Conditions will be 1) placebo; 2) oral dronabinol (10mg); and 3) combined hydromorphone and dronabinol (10mg). Measures will be repeated throughout the session to fully characterize the drug effects. Participants and staff will be kept blinded to the study medications under investigation, and participants will be informed in the consent form they may receive a combination of FDA-approved stimulants, benzodiazepines, opioids, cannabinoids, over-the-counter medications or placebo, though the participants will not actually be receiving stimulants, benzodiazepines, or over-the-counter drugs. All participants will be provided with transportation to and from the experimental sessions. Primary outcomes are measures of clinical pain, central sensitization, physical function and drug effects/adverse events. A subset of participants will undergo blood draws for pharmacokinetic (pK) profile. This will be voluntary and should aid recruitment as those that do not want an IV will still be allowed to participate in the study. We will aim to recruit 30 participants that volunteer to undergo IV/blood drawing procedures in order to characterize pK.

Phase 1: The initial Phase of this project will include hydromorphone at a dose of 4mg.

Phase 2: The second Phase of this project will include hydromorphone at a dose of 2mg in order to evaluate drug effects at a reduced opioid dose.

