Pain Testing: Subjects will complete quantitative sensory testing (QST) to comprehensively and systematically measure general pain sensitivity and central sensitization. This approach will provide data regarding the full range of analgesic effects possible, across a wide variety of psycho-physiologically-mediated, experimentally-induced measures of pain perception. Subjects will complete a baseline QST session prior to study drug administration on each experimental session day and the pain testing battery will be repeated approximately every 90 mins. The QST battery consists of threshold and tolerance, and temporal summation, and conditioned pain modulation (CPM) tests. The threshold responses will be conducted in randomized and counter-balanced order, and conditioned pain modulation will always occur last.

Threshold Responses will be assessed using thermal and pressure stimulation. *Thermal threshold:* All contact heat stimuli will be delivered using a peltier-element-based stimulator (Medoc, Israel). Two trials of heat pain threshold will be administered using a thermode that gradually increases in temperature from a pre-set baseline (31°C) until the subject indicates when the stimulus “first feels painful” (threshold, HPTh) and presses a button (which terminates the procedure) indicating that the pain is intolerable (tolerance, HPTo). *Pressure threshold:* Pressure pain thresholds (PPTh) will be determined at each of the following sites on both sides of the body using a pressure algometer (SBmedic; Sweden): the medial fat pad of the knee, patella, trapezius, and thumb. Pressure at the site is gradually increased at a steady rate and stopped when the subject indicates the stimulus is first perceived as painful. Thirty-second inter-stimulus intervals will be maintained. Trials will be averaged for one HPTh, HPTo, and PPTh measure.

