a. Primary outcome variable:

Aim 1: Evaluate the magnitude and duration of cannabinoid/opioid combination to reduce clinical pain (Hyp1) and central sensitization (Hyp2). Hyp1 (pain VAS) and Hyp 2 (CS) will be analyzed using repeated 2-factor (Drug x Time) models that examine linear and quadratic effects as well as duration and magnitude, and direct and interaction effects. If large variation exists across subjects at baseline, then raw data will be transformed to change-from-baseline and analyzed in drug condition by time models. A secondary outcome will be peak change from baseline, analyzed as a function of Drug (1-factor model).

- Aim 2: Evaluate the degree to which physical functioning is altered by the cannabinoid/opioid combination.** Hyp3 will be assessed using the TUG and 6MWT. Time to complete the TUG task will be the primary outcome and will be evaluated using 2-factor (Drug x Time: Pre to Peak) models.
- Aim 3: Conduct a direct comparison of the subjective, physiological, abuse liability, and cognitive effects of the cannabinoid, opioid, and combination.** Hyp4 (adverse events) will be assessed by summing the mean number of related mild, moderate, and severe adverse events (separately) and using 1 factor models to assess a main effect of Drug. Hyp5 (abuse liability) will be assessed using the Drug vs. Money questionnaire and changes in VAS ratings using 2-factor models (Drug x Time). Hyp6 will evaluate changes in neurocognitive performance, including study session number as a covariate to control for practice effects, using 2-factor (Drug x Time) analyses. Secondary outcomes for this hypothesis will be analysis of peak change from baseline for the cognitive outcomes, analyzed using 1-factor (Drug) ANOVAs to evaluate a main effect of drug.

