- Aim 4: Evaluate the pharmacokinetic (pK) and pharmacodynamic (pD) profile of the cannabinoid, opioid, and the combination in OA patients.** Hyp 7 (pK) will be assessed by evaluating Cmax (maximum concentration) and Tmax (time to maximum concentration) as a function of Drug condition using 1-factor models. We will also examine linear and quadratic effects to evaluate the time course of concentration. Linear and quadratic effects will be modeled for Hyp8 (pD) and analyzed by evaluating VAS and physiological ratings, transformed to change from baseline, evaluating area under the curve and peak change from baseline to identify main effects of the Drug condition. We will then conduct multivariate regression analyses to evaluate the degree to which the Cmax and Tmax correlate with pharmacodynamic outcomes, including abuse liability ratings, VAS ratings of drug effects, and cognitive testing outcomes.

Statistical analyses will be conducted separately by Phase and use multilevel analyses with an autoregressive (AR1) or compound symmetry (CS) covariance structures (as appropriate for the data set) using SAS PROC MIXED¹³⁷. Interpretation of drug condition main effects and interactions will rely on Tukey post-hoc tests. Statistical significance will be set at $p < 0.05$.

Expected Outcomes: We expect that dronabinol will enhance hydromorphone-induced analgesia to both clinical and laboratory-evoked pain. Our comprehensive battery of rigorous, testing procedures provides an opportunity to test effects on multiple mechanisms of experimentally-induced pain. We also expect improvement in physical functioning under combined dosing, and that the addition of the cannabinoid will not significantly increase the overall abuse liability or adverse event profile. We do suspect the cannabinoid may have cognitive effects (though the degree to which this may happen is not clear).

b. Secondary outcome variables.

Demographic and drug use characteristics that are hypothesized a priori to be associated with outcomes (e.g., Body Mass Index) will be compared across sex groups and significant differences will be included as covariates in the subsequent analyses. All analyses will be repeated and sex (male/female) will be added as a factor to the analyses.

c. Statistical plan including sample size justification and interim data analysis.

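### The plan states no session-level covariance, so Drug main-effect tests in the multi-time-point models can run well above 5% under some readings of its wording

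*Combined protocol and SAP*

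**What the plan says.** Under the Study Design Overview in section 4a, participants "will complete four different within-subject experimental sessions", one drug condition per session. Under Pain Testing, each session has a pre-dose baseline and "the pain testing battery will be repeated approximately every 90 mins". The number of time points is not given.

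In section 7a, pain VAS (Hyp1) and central sensitization (Hyp2) "will be analyzed using repeated 2-factor (Drug x Time) models", covering direct as well as interaction effects. The VAS part of Hyp5 and the cognitive outcomes of Hyp6 use the same form, and TUG uses "2-factor (Drug x Time: Pre to Peak) models". If baselines vary widely, "raw data will be transformed to change-from-baseline and analyzed in drug condition by time models".

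The covariance specification is one phrase at the end of section 7a: "multilevel analyses with an autoregressive (AR1) or compound symmetry (CS) covariance structures (as appropriate for the data set"). In that phrase CS means compound symmetry, not central sensitization. Tukey tests are to interpret Drug main effects and interactions, at a 0.05 significance level. The plan does not state the SUBJECT= level, any random effect, the denominator degrees of freedom, or how the structure will be chosen.

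**The concern.** Two readings taken an hour or two apart on the same day share whatever was particular to that day: the state of the knee, sleep, calibration, that session's baseline. Each drug is given to a participant on one day only, so this day-to-day variation belongs in the error term for a Drug main effect. Compound symmetry over all of a participant's observations gives same-session readings the same correlation as readings from different days. The repeated readings within a session then count as extra independent evidence about the drug, and the standard error for Drug is too small. At stake is the central claim that the combination differs from each drug alone and from placebo.

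**Working it through.** **Inputs.** From the documents: four drug conditions; alpha 0.05; 64 completers (section 7c), analysed separately by Phase, so 32 per Phase if 64 is the total. Assumed: T = 5 time points per session (range 2 to 7); s, the session variance as a share of within-participant variance, from 5% to 50%; complete data.

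**The nominal 5% is attainable.** For balanced data, F = MS(drug) / MS(drug x participant) on 3 and 3(n - 1) df gives 5.0% in 400,000 simulated draws.

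**Participant-level compound symmetry.** Scale the session plus residual variance to 1. With no drug effect:

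- E[MS drug] = E[MS drug x participant] = A = (1 - s) + T s, the latter on 3(n - 1) df.
- The within-session residual has expectation 1 - s on 4(n - 1)(T - 1) df.
- This structure pools the two: D = [3A + 4(T - 1)(1 - s)] / (4T - 1).
- The F statistic is too large by R = A / D. In large samples, type I error = P(chi-square on 3 df > 7.81 / R).

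For T = 5, D = [3A + 16(1 - s)] / 19:

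| s | A | D | R | Type I error |
|---|---|---|---|---|
| 0 | 1.00 | 1.000 | 1.00 | 5% |
| 0.05 | 1.20 | 0.989 | 1.21 | 9% |
| 0.10 | 1.40 | 0.979 | 1.43 | 14% |
| 0.30 | 2.20 | 0.937 | 2.35 | 34% |
| 0.50 | 3.00 | 0.895 | 3.35 | 51% |

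The sample size cancels from R, so enrolling more participants does not help; results for n = 32, 50 and 64 agree. A separate simulation at n = 32 gave 13%, 33% and 50% for s = 0.10, 0.30 and 0.50. Its Tukey family-wise error was 13%, 32% and 49%, so Tukey does not repair this. For s from 5% to 50% the range is 6% to 18% at T = 2 (the TUG case) and 11% to 63% at T = 7.

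**Change from baseline.** Subtracting a session's baseline removes any additive session effect, but every post-dose value in that session then carries the same baseline error. With independent residuals of variance v, each change has variance 2v and two changes in one session have covariance v. The correlation is v / 2v = 0.5, which is s = 0.50 with no true session effect. Five post-dose points give R = 3.35 and about 51% (49.5% when the model was fitted to simulated data). Four give A = 2.5, D = (7.5 + 6.0) / 15 = 0.90, R = 2.78 and about 42%.

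**Other readings of the sentence.** REML fits to simulated null data, 500 to 1,000 runs per cell; participant share of total variance 50% (30% in one scenario), autocorrelation where present 0.5 to 0.7:

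| Reading | Drug main-effect type I error |
|---|---|
| AR(1) over all of a participant's observations | about 1% with independent residuals; 14% with autocorrelated residuals; 25% on change from baseline |
| Better-fitting of participant-level AR(1) and compound symmetry | 10% to 33% with session-level correlation |
| Participant intercept + AR(1) across sessions | 17% to 25% with session-level correlation |
| Participant intercept + AR(1) within session | 6% to 15% with session-level correlation |
| Structure within session, no participant effect | about 0% on raw data; 6% (compound symmetry) or 12% (AR(1)) on change from baseline |
| Participant effect + compound symmetry within session | 4.0% to 6.8% (Monte Carlo standard error about 1 point) |

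**Drug x Time.** Its proper error is the within-session residual, 1 - s. Participant-level compound symmetry uses D instead, for example 0.937 against 0.70 at s = 0.30. The test is therefore conservative: 0% to 4% with session variance and about 5% without.

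**The case against.** The strongest reply is that the plan says multilevel, and the PROC MIXED reference it cites is titled for multilevel and hierarchical models. AR(1) or compound symmetry may then describe only the residuals, alongside random effects left unstated. This stands as far as it goes: a participant effect plus within-session compound symmetry is an admissible reading and holds about 5%. But no session term is written anywhere. The session-number covariate for Hyp6 adjusts the mean for practice and does not model a participant's day-to-day variation. Choosing structures to suit the data is no safeguard either, since picking the better-fitting participant-level structure still left 10% to 33%.

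A second reply is that each session includes a pre-dose baseline, so a drug effect should appear largely in Drug x Time, which is not inflated. That is correct, and it limits the damage in raw-data models. Section 7a nevertheless tests direct effects too and interprets Drug main effects with Tukey contrasts. In the change-from-baseline version the Drug main effect carries much of the drug comparison.

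A reader might infer that every Drug test in the plan is anti-conservative. The documents do not support that. Peak change, adverse-event counts, Cmax and Tmax, and Drug vs. Money (completed at the final assessment each day) give one value per session, which a participant effect represents properly. Some readings of the sentence err in the conservative direction.

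**Conclusion.** The model is under-specified in a way that matters: the same sentence permits analyses whose Drug main-effect type I error runs from about 0% to about 50%. The exposed tests are the Drug main effect and its Tukey contrasts for Hyp1, Hyp2, the VAS part of Hyp5 and Hyp6, and to a lesser degree pre-to-peak TUG.

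The 13% to 50% range is conditional on participant-level compound symmetry, five time points and session shares of 10% to 50%; the documents supply neither the time points nor the shares. The change-from-baseline figure of about 40% to 50% needs no session variance, but it assumes independent residuals and four or five post-dose points. None of these figures can be read as the trial's actual error rate, because the plan does not commit to the model that produces them.

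**What to change.** Prespecify the PROC MIXED model by type of outcome:

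- **Multi-time-point Drug x Time models, raw or change from baseline:** a random intercept for participant and one for session within participant (equivalently, compound symmetry within session), with Kenward-Roger degrees of freedom. Allow AR(1) residuals within session (SUBJECT=participant*session) only in addition to the session term, and only with at least three time points.
- **Pre-to-peak TUG:** participant and session intercepts without AR(1). A homogeneous covariance for two time points has two parameters (a variance and a covariance). A session intercept plus AR(1) residuals needs three, so it cannot be estimated.
- **One value per session:** a participant effect alone, since a session effect cannot be separated from the residual.

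Replace the open choice between AR(1) and compound symmetry with these rules. The checks above cover participant plus within-session compound symmetry; the version with added AR(1) and the Kenward-Roger adjustment were not simulated.

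The cost is SAP wording and a little model code, with no change to design or data collection. The downside is wider, correctly calibrated intervals for Drug main effects.

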
2. Objectives (include all primary and secondary objectives)

Aim 1: Evaluate the magnitude and duration of cannabinoid/opioid combination to reduce clinical pain and central sensitization. We hypothesize the cannabinoid/opioid combination will increase the

magnitude and duration of analgesia in clinical pain report (Hyp1) and QST-derived central sensitization (Hyp2), relative to each drug administered alone and relative to placebo.

Aim 2: Evaluate the degree to which physical functioning is altered by the cannabinoid/opioid combination. We hypothesize that the drug combination will improve physical function (Hyp3) relative to the drugs administered alone and placebo.

Aim 3: Compare the subjective, physiological, abuse liability, and cognitive effects of the cannabinoid, opioid, and combination. We hypothesize that cannabinoids will not increase adverse events (Hyp4), or abuse liability (Hyp5: ratings of positive drug effects) relative to opioids alone and that the cannabinoid (alone and in combination with opioids) will reduce neurocognitive performance (Hyp6), relative to the opioid alone and placebo.

Aim 4: Evaluate the pharmacokinetic and pharmacodynamic profile of the cannabinoid, opioid, and the combination in OA patients. We hypothesize that the combined dose will result in an altered pharmacokinetic (Hyp7) /pharmacodynamics profile (Hyp8) compared to either drug alone.

3. Background (briefly describe pre-clinical and clinical data, current experience with procedures, drug or device, and any other relevant information to justify the research)

This laboratory study is the first step in addressing an important and timely public health problem: Can cannabinoids enhance the analgesic efficacy of an opioid and ultimately reduce opioid dosing in people with chronic pain?

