This will be the first study to examine interactions between cannabinoids and opioids on clinical and laboratory-evoked measures of pain in a population who has chronic pain and central sensitization. The study uses a within-subject, placebo-controlled design and no data exist upon which to generate a power analysis. We have selected two primary outcomes for the measurement of analgesia: measures of conditioned pain modulation and time to hand withdraw latency in a cold presser test.

[name], a biostatistician with extensive experience analyzing within-subject laboratory tests of drug effects, conducted a revised power calculation based on new literature that employs methods similar to those of this study (Cooper et al., 2018). Sample size estimates were premised with a power of 0.8, alpha =0.05 and calculated effect sizes (Cohen, 1988). These analyses suggests a sample size ranging from 10-15 individuals would be sufficient to detect large effect sizes. Because one of our aims focuses on a sex-comparison, we originally planned to double our enrollment. Thus, our sample of 64 completers (32/sex) will yield sufficient power to evaluate direct effects of study condition on CPM and cold presser in both Phases, even at small effect size levels, and will also be sufficient to identify between-session differences on pK results¹⁴⁰.

d. Early stopping rules.

The safety of participants is the highest priority. The largest potential risk of this study is cardiovascular in nature. This notion is based upon the results of a published study that reported an increase in heart rate and blood pressure among patients exposed to the cannabinoid dronabinol who were also undergoing opioid withdrawal (of which increased heart rate and blood pressure is a known symptom). This group differs from our target population in many ways, however out of an abundance of caution in these early studies, we will use this experience to inform our safety criteria. We will monitor vital signs at all study data collection time points and will follow procedures that we have developed and successfully used in previous studies that administered drugs (e.g., cocaine) with known cardiovascular risks. Specifically, if a participant's parameters reach these thresholds, then a study physician, who will always be available via telephone, will be contacted and consulted to determine the appropriate course of action.

- Systolic blood pressure: $\geq 180\text{mm Hg}$

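### Tukey tests over all pairs spend power on comparisons that Hyp1 to Hyp3 do not ask about; prespecify the three contrasts with the combination

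*Combined protocol and SAP*

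**What the plan says.** Section 2 (Objectives) states Hyp1 and Hyp2 as the combination increasing analgesia "relative to each drug administered alone and relative to placebo". Hyp3, on physical function, names the same three comparators. Hyp6 differs: it compares dronabinol alone, as well as the combination, with hydromorphone and with placebo.

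Section 7a analyses each Phase separately, uses Drug x Time models for Hyp1 to Hyp3, sets significance at 0.05 and adds: "Interpretation of drug condition main effects and interactions will rely on Tukey post-hoc tests". It defines no family of comparisons, either for the four-condition main effect or for the Drug x Time cells.

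Section 7c says: "Sample size estimates were premised with a power of 0.8, alpha =0.05 and calculated effect sizes". It then reports: "These analyses suggests a sample size ranging from 10-15 individuals would be sufficient to detect large effect sizes". The planned sample is described so: "Thus, our sample of 64 completers (32/sex) will yield sufficient power to evaluate direct effects of study condition on CPM and cold presser". That claim is made for each Phase and is said to extend to small effects. Section 7c does not say whether the sized test was the overall Drug test or a pairwise contrast, whether it was one- or two-sided, or whether any multiplicity adjustment was made.

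**The concern.** Three contrasts sharing one reference condition form a many-to-one problem. Tukey solves a wider one: it protects every pair among four conditions, so the three contrasts that decide Hyp1 to Hyp3 share the error allowance with hydromorphone versus dronabinol, hydromorphone versus placebo and dronabinol versus placebo. A larger critical value is then applied to the lead hypotheses with no added protection for the questions they pose. Because each Phase is analysed on its own, the smaller per-Phase sample bears the cost.

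The success rule is also open. If Hyp1 is to be claimed only when the combination beats all three comparators, that requirement already controls the error, and any adjustment within the hypothesis is unnecessary.

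**Working it through.** **Inputs.** Four within-person conditions (Section 4a and Tables 1a and 1b); three contrasts (Section 2); level 0.05 and analysis by Phase (Section 7a); sizing at power 0.8 and alpha 0.05 (Section 7c). People per Phase is not fixed: 64 completers over two Phases gives 32; the 100 participants in the Study Design Overview, split equally, give 50; reading 64 as a per-Phase figure gives 64 (which would need 128 people in all, more than the 100). Effect sizes are assumptions, because Section 7c gives none: d is the mean within-person difference divided by the SD of that difference.

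**1. The plan's own figure.** Take large to mean d = 0.8 or f = 0.4 (assumed), with no adjustment.
- Paired comparison, normal approximation, two-sided: ((1.960 + 0.842)/0.8)² = 12.3, so 13; one-sided: ((1.645 + 0.842)/0.8)² = 9.7, so 10.
- Paired t-test: 15 two-sided, 12 one-sided.
- Overall Drug test, four repeated levels, f = 0.4: 14 at a between-session correlation of 0.3, 10 at 0.5.

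The stated 10 to 15 is therefore reproduced by either a pairwise or an overall test, and cannot show which was meant.

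**2. Pairs.** 4 × 3/2 = 6 pairs, of which 3 involve the combination.

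**3. Critical values.** Degrees of freedom are 3(n − 1). Tukey: q(0.95; 4, df)/√2. Dunnett: two-sided, three contrasts with correlation 0.5.

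| n per Phase | df | Unadjusted | Tukey | Dunnett |
|---|---|---|---|---|
| 32 | 93 | 1.986 | 2.616 | 2.388 |
| 50 | 147 | 1.976 | 2.599 | 2.373 |
| 64 | 189 | 1.973 | 2.592 | 2.368 |

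Per-pair alpha is about 0.0103 to 0.0104 with Tukey and 0.0189 to 0.0190 with Dunnett.

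**4. Power per contrast** (non-central t, non-centrality d√n), unadjusted / Tukey / Dunnett, %:

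| n per Phase | d = 0.4 | d = 0.5 | d = 0.8 |
|---|---|---|---|
| 32 | 61.0 / 36.7 / 45.3 | 79.9 / 58.5 / 67.0 | 99.4 / 97.0 / 98.3 |
| 50 | 80.2 / 59.2 / 67.5 | 94.0 / 82.4 / 87.6 | 100 / 99.9 / 99.9 |
| 64 | 88.9 / 72.8 / 79.6 | 97.8 / 91.9 / 94.8 | 100 / 100 / 100 |

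Hand check at n = 32, d = 0.5: 0.5 × √32 = 2.828; Φ(2.828 − 2.616) = 0.58 for Tukey and Φ(2.828 − 2.388) = 0.67 for Dunnett. Dunnett minus Tukey runs from 2.9 points (n = 64, d = 0.5) to 8.6 points (n = 32, d = 0.4), and is at most 1.3 points at d = 0.8.

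**5. All three contrasts must succeed.** Simulated with equal effects and correlation 0.5, unadjusted / Tukey / Dunnett: n = 32, d = 0.5: 61 / 33 / 43%; n = 50, d = 0.4: 62 / 34 / 44%. Equal effects against all three comparators is an assumption that the documents do not support, so these figures only illustrate the direction and rough size.

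**6. People needed for 80% power per contrast**, same method, unadjusted / Tukey / Dunnett: d = 0.8: 13 / 20 / 17; d = 0.5: 33 / 48 / 42; d = 0.4: 50 / 74 / 65.

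**7. Drug x Time.** Hyp3 uses two times (pre and peak), so 4 × 2 = 8 cells. If Tukey were run over all cells there would be 8 × 7/2 = 28 pairs at about 0.0025 each. The plan does not say whether that is intended.

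**The case against.** Tukey is a legitimate choice: it holds the familywise rate at 0.05, and no error-control failure has been shown. The gain from Dunnett is modest at moderate effects and vanishes at large ones. At 0.5 SD, Tukey already exceeds 80% power with 50 or 64 people per Phase; only the reading of 32 leaves it well short. All of this stands, and it limits the point to efficiency.

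The other three pairs are not idle either. Section 6 wants to learn whether dronabinol's effect on hydromorphone analgesia is additive, synergistic or absent, which also needs each single drug against placebo. Hydromorphone versus placebo shows whether the pain measures respond to an active drug, and Hyp6 uses contrasts of dronabinol alone. This stands too, and is why those pairs should stay as tests and not become mere description.

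A reader might go further and infer that Tukey conflicts with the alpha of 0.05 used for sizing. The documents do not support that. Tukey's familywise level is itself 0.05, Section 7c does not say whether an overall or a pairwise test was sized, and the stated 10 to 15 fits both. Section 7c also names CPM and cold pressor, whereas Section 7a assigns pain VAS, the central sensitization index and TUG to Hyp1 to Hyp3. What can be said is conditional: if 10 to 15 was meant for a pairwise contrast at d = 0.8, six-pair Tukey would need about 20, a number that every reading of the planned per-Phase sample exceeds.

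**Conclusion.** The point holds as one of efficiency and specification. Hyp1 to Hyp3 name three contrasts each, and six-pair Tukey costs about 3 to 9 points of power per contrast against a matched three-contrast family. That rests on assumed effects of 0.4 to 0.5 SD, 32 to 64 people per Phase, a common SD for all pairwise differences, and Tukey being applied to the six main-effect pairs, which is the natural reading but is not written down. If all three contrasts must succeed, which is how the wording of Section 2 most naturally reads, the power lost to Tukey is larger, since testing each at 0.05 would suffice. For Drug x Time the cost could also be larger, but it cannot be fixed until the family is stated. Nothing here invalidates the planned analysis; it should be changed because the gain needs only wording.

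**What to change.** In Section 7a, for Hyp1 to Hyp3:

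1. Prespecify three contrasts with the combination as reference: versus hydromorphone, versus dronabinol, versus placebo.
2. Write them as explicit contrasts of the Drug effect and of the Drug x Time effect, for example the pre-to-peak change under the combination minus the pre-to-peak change under each comparator, and say which of the two decides each hypothesis. Setting ADJUST=DUNNETT on the Drug x Time cell means is not enough: it compares every cell with one control cell, not the combination with each comparator.
3. State the success rule. If a hypothesis is claimed only when all three contrasts succeed, say so and test each at 0.05. If any single contrast may support a claim, use a Dunnett-type adjustment over the three. Bonferroni over three is a simple substitute (65.2% against 67.0% at n = 32, d = 0.5).
4. Keep Tukey for the remaining pairs, including hydromorphone and dronabinol each against placebo, as secondary tests, and for Hyp6.
5. In Section 7c, state whether the sized test was overall or pairwise, and with what adjustment.

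The cost is a few lines of wording and contrast code, with no added data or participants. The small downside is that the pairs without the combination become secondary for Hyp1 to Hyp3.
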